6.4 STUDY INTERVENTION/EXPERIMENTAL MANIPULATION ADHERENCE

N/A - This study does not involve intervention.

6.5 CONCOMITANT THERAPY

6.5.1 RESCUE THERAPY

Participants are allowed to continue any therapy (including speech-language therapy) that they are receiving at the time of the study. Because this trial involves no intervention, concomitant therapy will not impact the trial results. The study team will not dispense rescue therapy.

7 STUDY INTERVENTION/EXPERIMENTAL MANIPULATION DISCONTINUATION AND PARTICIPANT DISCONTINUATION/WITHDRAWAL

7.1 DISCONTINUATION OF STUDY INTERVENTION/EXPERIMENTAL MANIPULATION

If the study term observes several time periods of missed trials, they will address the issue with a participant during the weekly check-in. As feasibility is the cornerstone of this trial, the study team will not discontinue participants for reasons related to protocol adherence.

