For three weeks, PWA will name aloud pictures that appear on the smartwatch as they go about their daily activities. At the end of each week, PWA will complete a virtual check-in with the study team at which time they will also complete a brief (16-item) Qualtrics survey about their EMA experiences that week.

Version 1.000

Protocol 15 March 2022

Post-EMA Protocol Testing	In a final session, PWA will complete the overt object
and Exit Interview	naming test in standard SLP format once more. Finally,
	they will participate in an exit interview about the study.

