Retention Team, we will also develop and implement strategies to ensure recruitment of participants of color. One strategy will be to maximize engagement with Hispanic/Latinx and Asian PWA involved in an active clinical trial conducted by the BU Aphasia Research Lab on bilingual aphasia recovery. Given our multipronged approach, the large pool of potential participants, and expected high interest in the study, we anticipate having a waitlist of potential participants. Thus, a second approach will be to prioritize participation of PWA of color on the waitlist to ensure their necessary inclusion in this study. All efforts will be made to maximize retention of enrolled participants. We will do so by: (1) careful screening of potential participants in which we explain in detail the procedures (e.g., protocols, time commitment) and provide time and opportunity for addressing the questions/concerns of participants and/or care providers, (2) providing flexible scheduling options and assistance with arranging transportation as needed, and (3) weekly contacts in weeks 2-4 during the EMA/μEMA protocols with PWA and/or their care providers.

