6 STUDY INTERVENTION(S) OR EXPERIMENTAL MANIPULATION(S)

6.1 STUDY INTERVENTION(S) OR EXPERIMENTAL MANIPULATION(S) ADMINISTRATION

6.1.1 STUDY INTERVENTION OR EXPERIMENTAL MANIPULATION DESCRIPTION

Participants will be pseudo-randomly assigned to either the 1-item EMA condition (n = 10) or 9-item EMA condition (n = 10). For every prompt, the smartwatch will vibrate to alert the participant to a prompt to complete either a single picture naming trial (in the 1-item condition) or a set of picture naming trials (in the 9-item EMA condition). Participants in both conditions will be scheduled to complete 36 overt picture naming trials per day for three weeks. The only difference between conditions will be the trial delivery schedule: PWA in the 1-item condition will complete a single naming trial at a time, 36 times per day whereas PWA in the 9-item EMA condition will receive four prompts per day to complete a set of nine picture naming trials per prompt. The twofold rationale for comparing 1-item and 9-item EMA conditions is that we will be able to ensure the results reflect the viability of either delivery schedule specifically and not just the novelty of smartwatch use, and this approach will provide preliminary data regarding which method works best for which PWA.

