6.3 MEASURES TO MINIMIZE BIAS: RANDOMIZATION AND BLINDING

PWA will be pseudo-randomly assigned to either the 1-item or 9-item EMA condition. This quasi-randomization will be done to ensure the conditions are balanced for overall aphasia severity. No blinding will be performed.

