8.1 ENDPOINT AND OTHER NON-SAFETY ASSESSMENTS

Endpoint Assessments: Feasibility will be classified in three ways: (1) PWAs' adherence to the smartwatch μΕΜΑ or EMA protocol via compliance and completion, (2) PWAs' perceived burden of completing the EMA protocol, and (3) speech intelligibility of recorded naming attempts. Currently, PWAs' capacity for adhering to a smartwatch EMA protocol via button press responses or verbal responses is unknown. As such, compliance will be based on the number of YES button responses to the "Ready?" screen whereas completion will be based on naming attempts. Specifically, similar to [name] et al. (2016), compliance will be determined by the number of YES responses over scheduled trials, including trials missed due to the watch being off/uncharged. Completion will be calculated as trials with captured audio (reflecting attempted naming) over delivered trials, excluding trials missed to the watch being off/uncharged. Perceived burden will be measured via responses to the weekly surveys during weeks 2-4. Finally, speech intelligibility will be measured by a categorical rating of responses captured in each audio clip (i.e., completely intelligible, partially intelligible, or completely unintelligible).

Other Non-Safety Assessments: Before the EMA period, PWA will be administered the following testing battery. The Quick Aphasia Battery (QAB) will be used as our eligibility assessment and to measure overall aphasia severity. The Pattern Comparison Processing Speed Test and Flanker Inhibitory Control and Attention Test from the NIH Cognition Toolbox will be used to measure non-linguistic visual attention and executive functions, respectively. We will use brief, standardized picture description and story elicitation tasks from the AphasiaBank protocol to index anomia in discourse. Participants will complete an overt object naming test twice before EMA and once after EMA so that the research team can evaluate word retrieval via the standard SLP assessment format (i.e., single administration in a quiet 1:1 interaction). This picture naming probe will include normed real photos of the 260 items from the Snodgrass and Vanderwart stimuli set. Before EMA, PWA will also participate in an intake interview and complete a questionnaire about their comfort with technology, adapted for aphasia (simple language, short phrases).

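### Section 7.1 lets an unblinded team act on missed trials while compliance and completion are accruing, under an undefined trigger that can fire differently by arm

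*Combined protocol and SAP*

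**What the plan says.** Section 7.1 provides for contact prompted by poor response: "If the study term observes several time periods of missed trials, they will address the issue with a participant during the weekly check-in". It does not say how many periods count, how long a period is, whether it must be wholly missed, or what the conversation contains. The same section states that "the study team will not discontinue participants for reasons related to protocol adherence", so contacted participants stay in the analysis.

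Section 6.3 states "No blinding will be performed". Section 1.3 puts a check-in at the end of each EMA week and attaches the burden survey to it: "PWA will complete a virtual check-in with the study team at which time they will also complete a brief (16-item) Qualtrics survey". The order of survey and conversation is not given. Section 5.5 lists as a retention measure "weekly contacts in weeks 2-4 during the EMA/μEMA protocols with PWA and/or their care providers".

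Compliance and completion are the primary endpoints (1.1, 3). Under 8.1, "compliance will be determined by the number of YES responses over scheduled trials, including trials missed due to the watch being off/uncharged". Section 9.1 hypothesises higher compliance and completion in the 1-item condition. The model in 9.4.2 has condition as its only fixed effect, plus random effects of participant and trial. No log of contacts and no analysis of the weeks before contact is planned.

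**The concern.** A missed trial is a zero on the compliance outcome. Section 7.1 lets that outcome prompt a staff contact that may change later values of the same outcome. The staff know the condition and judge for themselves when the trigger is met. Compliance and completion after the first check-in are therefore measured under outcome-triggered contact, and the planned analysis cannot separate those weeks from week 1.

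Two results are at stake. The first is the feasibility figure itself, meant to show what people with aphasia do with this protocol. The second is the contrast between conditions, because the trigger need not act equally on the two delivery schedules. Burden, a secondary endpoint compared between conditions in 9.4.3, may also be rated just after a conversation about missed trials.

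**Working it through.** **Inputs.** From 6.1.2: 36 trials a day for three weeks (756). The 9-item arm gets four prompts a day, one per 2.5-hour block, so 28 blocks a week with nine trials each. The 1-item arm gets 36 single prompts at random times, on average nine per 2.5 hours. From 9.2: 10 per arm, AR(1) correlation 0.600, alpha 0.05, 0.500 against 0.545, and an earlier difference above 0.20.

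**The plan's own figure.** The AR(1) inflation of a participant mean is 1 + 2Σ(1 − k/756)·0.6^k = 3.990. Effective n per arm is 7560/3.990 = 1894.7. A two-sided comparison of 0.500 with 0.5455 (OR 1.20) has power 0.800 (0.792 with 0.545), so the stated 80% reproduces.

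**Trials exposed.** Check-ins fall at the end of weeks 1, 2 and 3. The third follows the last trial, so the first two matter: 2 × 7 × 36 = 504 of 756 trials, or 0.667.

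**How the trigger acts by arm.** Assume equal trial-level compliance p in both arms, q = 1 − p, nine 1-item prompts per block, and 9-item sets answered or missed whole. In the 9-item arm both readings give 28q blocks a week. In the 1-item arm:

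- Independent misses: wholly missed 28q^9; any miss 28(1 − p^9).
- Beta-binomial, s = (1 − ICC)/ICC: wholly missed 28·Π(qs + i)/(s + i), i = 0 to 8; any miss 28·[1 − Π(ps + i)/(s + i)].
- AR(1) 0.6: wholly missed 28·q(q + 0.6p)^8; any miss 28·[1 − p(p + 0.6q)^8].

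| Blocks per week that count | 9-item | 1-item, independent | 1-item, ICC 0.3 | 1-item, ICC 0.5 | 1-item, AR(1) 0.6 |
|---|---|---|---|---|---|
| Wholly missed, p = 0.75 | 7.0 | 0.0001 | 0.39 | 1.47 | 0.40 |
| Any miss, p = 0.75 | 7.0 | 25.9 | 18.8 | 14.9 | 19.0 |
| Wholly missed, p = 0.50 | 14.0 | 0.05 | 2.38 | 5.19 | 2.35 |
| Any miss, p = 0.50 | 14.0 | 27.9 | 25.6 | 22.8 | 25.7 |

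The order of the arms reverses with the reading. The ICCs are assumptions; 0.6 is the plan's value.

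**Watch-off periods.** These blank blocks in both arms. If a share w of blocks is watch-off, the ratio of wholly missed blocks (9-item to 1-item, independent misses otherwise) is [w + (1 − w)q]/[w + (1 − w)q^9]. With w = 0.05 and q = 0.5 it is 0.525/0.0519 = 10.1. With w = 0.20 and q = 0.2 it is 0.36/0.200 = 1.8. The gap narrows but does not close.

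**Size needed to matter.** A lift u in one arm over weeks 2-3 changes its overall compliance by 0.667u. Offsetting 0.045 takes 0.045/0.667 = 0.0675 (0.068 for the unrounded 0.0455). Offsetting 0.20 takes 0.20/0.667 = 0.30.

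**Week 1 alone.** With 252 trials the inflation is 3.970 and effective n per arm is 2520/3.970 = 634.7. Power for OR 1.20 is 0.37, the difference detectable with 80% power is about 0.079, and power for 0.70 against 0.50 is above 0.99. These figures inherit the plan's AR(1) assumption.

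**The case against.** Section 7.1 states one rule for everyone, weekly contact is planned for both conditions, and the conversation may be no more than charging or device troubleshooting. Watch-off periods are the most natural stretches of missed trials, and they occur in both arms. That is fair. It means the documents do not establish coaching, only an unspecified contact. It does not remove the problem: 8.1 counts watch-off misses in compliance, so even a reminder to charge the watch can raise the outcome.

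A reader might infer that the trigger fires far more readily in the 9-item arm and so pulls the contrast toward zero. The text does not settle this. It never says a period must be wholly missed, and 6.1.2 defines 2.5-hour blocks only for the 9-item arm. If any miss counts, the 1-item arm is contacted more. Even on the whole-block reading both arms may be contacted: at 50% compliance and ICC 0.5, a 1-item participant has 5.19 wholly missed blocks a week.

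A reader might also see a contradiction with 6.1.1, which says "The only difference between conditions will be the trial delivery schedule". That sentence describes how trials are delivered. A common rule with unequal firing rates is not a second assigned difference. Nor do the documents show that burden ratings are affected; they only leave the order open.

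Finally, an effect near the earlier study's 0.20 would survive any plausible contact effect. That stands, and it limits the severity.

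**Conclusion.** The point holds as a design weakness that should be fixed. Up to 504 of 756 trials per participant are observed under contact triggered by the primary outcome, from unblinded staff, with no definition, log or model term. Absolute feasibility in weeks 2-3 is then compliance with feedback of unknown frequency.

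For the contrast, the trigger can act very unequally on the two arms, but the direction is unknown because it depends on an undefined phrase. A lift of about 0.07 confined to one arm over weeks 2-3 is as large, overall, as the difference the trial is powered for; it could hide that difference or create it, depending on the arm. About 0.30 would be needed to offset 0.20. The documents give no evidence of how large a contact effect would be. The block counts rest on equal compliance, the assumed within-block correlations and nine prompts per block in the 1-item arm.

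**What to change.** 1. In 7.1, give every participant in both conditions the same scripted technical check-in, whatever their missed trials. If an adherence-triggered contact is kept, define it as a share of scheduled trials missed over a fixed window, identical in both arms, and log each contact.
2. In 1.3 and 8.1, have the burden survey completed before any discussion of missed trials.
3. In 9.4.2, report compliance and completion by week and condition, with EMA week 1 (before any check-in) as a supportive sensitivity estimate. Report logged contacts by arm.
4. Leave the lost-to-follow-up contacts in 7.3 and the safety communications in 8.4.3 unchanged.

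The cost is a reworded 7.1, a short script, a contact log and one extra table; no added visits. Some poor responders get less individual encouragement, so observed compliance may be somewhat lower. The week-1 estimate is less precise (about 37% power for OR 1.20, above 99% for a 0.20 difference, on the plan's inputs). Week 1 may also carry smartwatch novelty, so it should support the three-week analysis and not replace it.

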7.2 PARTICIPANT DISCONTINUATION/WITHDRAWAL FROM THE STUDY

Participants are free to withdraw from participation in the study at any time upon request. If a participant withdraws, the study team will obtain the reason(s) for withdraw. An investigator may discontinue a participant from the study for the following reasons: (1) Lost-to-follow up; unable to contact subject (see Section 7.3, Lost to Follow-Up), and (2) any event or medical condition or situation occurs such that continued collection of study data would not be in the best interest of the participant or might require an additional EMA period that would confound the interpretation of the study.

7.3 LOST TO FOLLOW-UP

A participant will be considered lost to follow-up if they fail to return for three scheduled check-ins or sessions and study staff are unable to contact the participant after at least 3 attempts. The following actions will be taken if a participant fails to return to the lab for a required study visit:

- The site will attempt to contact the participant, reschedule the missed visit or check-in, counsel the participant on the importance of maintaining the assigned visit schedule, and ascertain if the participant wishes to and/or should continue in the study
- Before a participant is deemed lost to follow-up, the investigator or designee will make every effort to regain contact with the participant (where possible, 3 telephone calls and/or emails). These contact attempts will be documented in the participant's study file.
- Should the participant continue to be unreachable, they will be considered to have withdrawn from the study with a primary reason of lost to follow-up.

15 March 2022

8 STUDY ASSESSMENTS AND PROCEDURES

Protocol

8.1 ENDPOINT AND OTHER NON-SAFETY ASSESSMENTS

Endpoint Assessments: Feasibility will be classified in three ways: (1) PWAs' adherence to the smartwatch μΕΜΑ or EMA protocol via compliance and completion, (2) PWAs' perceived burden of completing the EMA protocol, and (3) speech intelligibility of recorded naming attempts. Currently, PWAs' capacity for adhering to a smartwatch EMA protocol via button press responses or verbal responses is unknown. As such, compliance will be based on the number of YES button responses to the "Ready?" screen whereas completion will be based on naming attempts. Specifically, similar to [name] et al. (2016), compliance will be determined by the number of YES responses over scheduled trials, including trials missed due to the watch being off/uncharged. Completion will be calculated as trials with captured audio (reflecting attempted naming) over delivered trials, excluding trials missed to the watch being off/uncharged. Perceived burden will be measured via responses to the weekly surveys during weeks 2-4. Finally, speech intelligibility will be measured by a categorical rating of responses captured in each audio clip (i.e., completely intelligible, partially intelligible, or completely unintelligible).

Other Non-Safety Assessments: Before the EMA period, PWA will be administered the following testing battery. The Quick Aphasia Battery (QAB) will be used as our eligibility assessment and to measure overall aphasia severity. The Pattern Comparison Processing Speed Test and Flanker Inhibitory Control and Attention Test from the NIH Cognition Toolbox will be used to measure non-linguistic visual attention and executive functions, respectively. We will use brief, standardized picture description and story elicitation tasks from the AphasiaBank protocol to index anomia in discourse. Participants will complete an overt object naming test twice before EMA and once after EMA so that the research team can evaluate word retrieval via the standard SLP assessment format (i.e., single administration in a quiet 1:1 interaction). This picture naming probe will include normed real photos of the 260 items from the Snodgrass and Vanderwart stimuli set. Before EMA, PWA will also participate in an intake interview and complete a questionnaire about their comfort with technology, adapted for aphasia (simple language, short phrases).

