1 PROTOCOL SUMMARY

1.1 SYNOPSIS

Title: Word Retrieval in the Wild: An Ecological Momentary

Assessment Pilot Study in People with Post-Stroke Aphasia

Grant Number: UL1 TR002544

Study Description: People with post-stroke aphasia (PWA) suffer from anomia, a condition

where they know what they want to

say but cannot retrieve the words. For PWA, word retrieval changes

moment-to-moment, leading to diminished

motivation to participate in conversations and disengagement from

social interactions. In the real world, anomia

variability and severity are compounded by contextual factors of

communication exchanges (noise, dual-tasking).

Ecological momentary assessment (EMA) involves in-situ measurement

of a behavior over time during everyday

life. EMA has promise for capturing real-world anomia, yet EMA

methods have not been tested in PWA.

To target in-situ anomia, PWA will complete 36 picture-naming

trials/day for three weeks,

delivered either as a single trial 36 times per day (1-item EMA condition) or in four sets of nine trials/set per day (9-item EMA condition). Prior to completing community/home-based EMAs, participants will undergo standardized testing and smart device training. During the EMA period, participants will complete a brief survey about their EMA experiences at the end of each week. Following completion of the EMA protocol, participants will complete one final

assessment and exit interview session.

Objectives*: Primary Objective: To evaluate the feasibility of ecological

momentary assessment (EMA) of naming abilities in people with post-stroke aphasia

Secondary Determine relationships between feasibility

Objectives: metrics and personal factors

Endpoints*: Primary Endpoint: Compliance and completion over a 3-week

EMA protocol

Secondary Perceived burden of completing EMAs

Endpoints: during the 3-week protocol

Study Population: Individuals with post-stroke aphasia

Phase* or Stage: Chronic stroke (at least 6 months after stroke onset)

Description of Sites/Facilities Enrolling Participants:

Participants will be recruited through The Aphasia Network (TAN) Lab at Northeastern University.

[figure not shown]
Description of Study Manipulation:

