6.1.2 ADMINISTRATION AND/OR DOSING

In each condition, the smartwatch will vibrate to alert PWA to a single naming trial (1-item condition) or naming trial set (9-item EMA condition). After the vibration alert, PWA will see a screen that says "Ready to name a picture?" (1-item condition) or "Ready to name some pictures?" (9-item EMA condition). If the participant taps YES, a picture will appear, and the device will begin recording audio. PWA will have up to five seconds to provide an oral response, after which a "Thanks!" screen will appear. The fivesecond response window was selected based on research showing that PWA correctly name pictures within 3.5 seconds, on average, with longer response latencies for incorrect responses. If a participant fails to respond to a vibration prompt or pushes the NO button to the "Ready?" screen, they will be reprompted five minutes later via one more vibration alert. During the three-week EMA protocol, each participant will attempt to name 108 unique objects derived from the 260-item Snodgrass and Vanderwart photoset. The subset of pictures presented to each participant will be based on their naming evaluation (during week 1, session 1). When possible, half of the pictures will be items the PWA named correctly during the evaluation, and the other half will be incorrectly named pictures. This approach will allow us to gauge naming variability over time of items PWA are able versus unable to name during traditional SLP assessment, providing an important window into anomia. To mitigate practice effects, the individual pictures (1-item condition) or picture sets (9-item EMA condition) will be presented randomly without replacement until all 108 pictures have been presented, and then the picture cycle will restart. In both conditions, 36 naming trials will be scheduled per day, resulting in a total of 756 scheduled trials for each participant across the experiment. In the 1-item EMA condition, single-naming trial prompts will appear at random intervals from 10am to 8pm. In the 9-item EMA condition, PWA will receive four prompts per day to complete a set of nine picture naming trials per prompt; one prompt will be scheduled in every 2.5-hour block between 10am and 8pm.

15 March 2022

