6.2.1 INTERVENTIONIST TRAINING AND TRACKING

N/A - There is no intervention as part of this trial. Data used to calculate compliance, completion, and perceived burden will be automatically digitally recorded. Speech intelligibility ratings will be completed for all samples by one rater, and 20% of samples will be assessed by a second rater.

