9.4.2 ANALYSIS OF THE PRIMARY ENDPOINT(S)

We will code each trial in the EMA time series to index compliance, completion, and speech intelligibility. Every scheduled trial (n = 756 total trials) will be coded as 0 for a nonresponse/ NO button

Version 1.000

Protocol 15 March 2022

response or 1 for a YES button response, reflecting compliance. Every delivered trial with a naming attempt captured on audio (n trials will vary by person) will be coded as 0 for incomplete or 1 for complete, reflecting completion. For each of these measures, we will run a logistic mixed effects model with one of the feasibility measures (i.e., compliance, completion) as the dependent variable, condition (1-item vs. 9-item) as the independent variable, and random effects of participant and trial.

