9.4.3 ANALYSIS OF THE SECONDARY ENDPOINT(S)

Every audio clip (n trials will vary by person, depending on the number of naming attempts) will be coded as 0 for completely or partially unintelligible and 1 for completely intelligible, reflecting speech intelligibility. We will run a logistic mixed effects model with intelligibility as the dependent variable, condition (1-item vs. 9-item) as the independent variable, and random effects of participant and trial. For perceived burden, we will collect responses on three questions/survey for three weeks. Given the small amount of data, survey responses will be plotted to visualize trends in increasing/decreasing burden rather than compared statistically. We will statistically compared averaged burden ratings between participants in the 1-item vs. 9-item condition using t-tests or Wilcoxon rank sum tests (depending on the distribution of the data).

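### Completion treats captured audio as a naming attempt, but the YES tap starts the recording and no rule covers silent clips

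*Combined protocol and SAP*

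**What the plan says.** The synopsis (1.1) gives the primary endpoint as "Compliance and completion over a 3-week" EMA protocol. Section 8.1 explains why there are two measures. It is not known how well people with aphasia can respond by button or by voice, so compliance counts YES taps while "completion will be based on naming attempts". The operational rule follows: "Completion will be calculated as trials with captured audio (reflecting attempted naming) over delivered trials", leaving out trials missed because the watch was off or uncharged.

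Section 6.1.2 describes the device: "If the participant taps YES, a picture will appear, and the device will begin recording audio". It then allows a fixed window: "PWA will have up to five seconds to provide an oral response".

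Section 6.2.1 states: "Data used to calculate compliance, completion, and perceived burden will be automatically digitally recorded". Raters are named there only for intelligibility, with one rater for all samples and a second for 20%.

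The analysis sections use other wordings:
- **9.4.2:** "Every delivered trial with a naming attempt captured on audio (n trials will vary by person) will be coded as 0 for incomplete". The other code, 1, marks a complete trial. The meaning of incomplete is not given.
- **9.4.3:** every audio clip is "coded as 0 for completely or partially unintelligible and 1 for completely intelligible, reflecting speech intelligibility". The number of clips is tied to the number of naming attempts.
- **9.4.9:** completion is naming attempts over delivered trials, and intelligibility uses naming attempts as its denominator.
- **Section 3, objectives table:** completion is answered prompts over delivered prompts.

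Section 9.1 hypothesises intelligibility above 80% and higher completion in the 1-item condition.

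**The concern.** The two primary measures are meant to separate tapping from speaking. If a tap is enough to create a clip, and a clip is enough to count as complete, the second measure no longer isolates the verbal response. Word-finding failure could then appear as success on completion and as poor speech on intelligibility, although it is neither.

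The definitions also leave the numerator of a primary endpoint to be settled at scoring. Section 6.3 says that no blinding will be performed, so that choice could be made with condition known.

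**Working it through.** **1. The definitions side by side**

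| Section | Numerator of completion | Silent clip after a YES tap |
|---|---|---|
| 3 (table) | answered prompts | unclear: a tap or speech may count as an answer |
| 8.1 | trials with captured audio, glossed as attempted naming | counts on the rule, not on the gloss |
| 9.4.2 | trials coded 1 among those with an attempt on audio | no stated code |
| 9.4.9 | naming attempts | does not count if an attempt means speech |

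Section 9.4.2 also restricts the coded set to trials that already have an attempt on audio. Delivered trials without one then have no stated place in the model, although 8.1 and 9.4.9 keep them in the denominator.

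**2. Literal rule in the 1-item arm**

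Barring technical failure, each YES tap gives one clip. Completion is then YES/delivered and compliance is YES/scheduled. With 756 scheduled trials (9.4.2) and assumed counts of 680 delivered and 476 YES taps:
- compliance = 476/756 = 63.0%
- literal completion = 476/680 = 70.0%, whatever the silent share s of YES trials
- true attempted naming = 476(1 − s)/680, which is 63.0% at s = 10% and 56.0% at s = 20%

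**3. Intelligibility**

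If silent clips are coded 0, measured intelligibility = true intelligibility × (1 − s). It falls below 80% when s exceeds 1 − 0.80/true:
- true 85%: 1 − 0.80/0.85 = 5.9%
- true 90%: 1 − 0.80/0.90 = 11.1%
- true 95%: 1 − 0.80/0.95 = 15.8%

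**4. The plan's power figure, as a scale (9.2)**

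Inputs: 10 per group, 756 trials, AR(1) with ρ = 0.600, odds ratio 1.20, reference 0.500, alpha 0.05 (taken as two-sided; the plan does not say).
- Proportion for OR 1.20: odds 1.20, so 1.20/2.20 = 0.5455, against the plan's 0.545.
- Variance inflation = (1+ρ)/(1−ρ) − 2ρ(1−ρⁿ)/[n(1−ρ)²] = 4 − 1.2/(756 × 0.16) = 3.990.
- Effective trials = 756/3.990 = 189.5 per participant, or 1,894.7 per group.
- SE(log OR) = √[1/(1,894.7 × 0.25) + 1/(1,894.7 × 0.2479)] = 0.0651. Then z = 0.1823/0.0651 = 2.80, and power = Φ(2.80 − 1.96) = 80.0%. The stated figure reproduces.

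**5. Effect on the contrast, with assumed silent shares**

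Recorded completion = true attempts/(1 − s).
- Silent share in one arm only that equals the target difference: 1 − 0.500/0.5455 = 8.3%. In the 9-item arm it would hide a true 0.545 versus 0.500. In the 1-item arm it would create that difference from equal true rates of 0.500.

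With true attempts of 0.545 (1-item) and 0.500 (9-item):

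| s, 1-item | s, 9-item | Recorded | OR |
|---|---|---|---|
| 10% | 10% | 0.606 vs 0.556 | 1.23 |
| 5% | 10% | 0.574 vs 0.556 | 1.08 (power about 21%) |
| 10% | 20% | 0.606 vs 0.625 | 0.92 |

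Equal shares do little to the contrast; unequal shares can shrink or reverse it.

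**The case against.** The strongest reply is that the plan's intent is clear. Section 8.1 bases completion on naming attempts and glosses captured audio in that sense, and 9.4.2, 9.4.3 and 9.4.9 also speak of attempts. A silent clip holds no attempt, so a rater who left it out would be following those words. Section 6.2.1 may describe how data are captured rather than how they are scored, and 9.4.2 says the team will code each trial. Section 8.1 rates the responses in each clip, and silence is not a response.

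Much of this stands. A reader might infer that the plan scores silent trials as complete and as unintelligible; no section says so. A reader might also infer a bias toward the 9-item arm, because one tap there opens nine pictures. The documents do not describe the screens within a set and give no silence rate for either arm, so neither the existence nor the direction of such a bias is shown. If it did favour the 9-item arm, it would work against the hypothesis in 9.1. Nor is silence shown to be common: pictures named incorrectly at evaluation may still draw a spoken response. Finally, the model in 9.4.3 compares conditions and does not test the 80% figure.

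The reply does not supply the missing rule. The only operational rule given for an attempt is captured audio. No listening step is stated for completion, and neither the three rating categories nor the 0/1 code has a place for no response. Retained audio (10.1.4) allows re-scoring, but the choice of rule would then follow the data.

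**Conclusion.** The concern holds as a defect of definition in a primary endpoint. Followed literally, the stated rule lets silent or noise-only clips count as complete, and the intelligibility coding can absorb the same clips as 0. The definitions in sections 3, 8.1, 9.4.2 and 9.4.9 do not agree on what to do with them.

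The size is unknown. The thresholds of 5.9%, 11.1% and 15.8% for intelligibility assume true rates of 85%, 90% and 95% and that silent clips are scored 0. The 8.3% figure assumes silence in one arm only and takes the plan's own power inputs as given. These figures show that modest silent shares would matter. They do not show that such shares will occur, and the documents do not support saying that completion fails to measure attempted naming. The plan's 80% power figure is unaffected by this point.

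**What to change.** In 8.1, 9.4.2, 9.4.3, 9.4.9 and the objectives table, use one definition: a naming attempt is a clip in which the rater hears a verbal response from the participant. Then:
- The rater who already assesses all samples first records attempt present, yes or no.
- Completion is coded 1 if an attempt is present and 0 otherwise, over all delivered trials.
- Intelligibility is scored only on clips with an attempt.
- The attempt code is included in the existing 20% second rating, and agreement on it is reported.
- The share of YES trials without a verbal attempt is reported by condition.

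This should be settled before any clip is scored. It costs one yes/no code per clip and edits to five places. Completion will no longer be fully automatic and may come out somewhat lower.
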